9.2.4.5. Treatment of Atopic Dermatitis with Abrocitinib

At the baseline visit (Visit 1) reason of starting or re-starting treatment with abrocitinib will be documented. At each visit (Visit 1-6) dose of treatment with abrocitinib and reason for its choice will be documented. If an escalation or a de-escalation of dosage occurred since the last visit, in addition stop date of previous dosage, start date of new dosage and reason for switch (lack of efficacy or intolerability) will be documented.

If treatment with abrocitinib got terminated since the last visit, reasons for ending abrocitinib treatment, stop date of treatment, start date of other new treatment and reason for switch (lack of efficacy or intolerability) will be documented.

At Visits 2-6, the investigator will ask the patient for his or her self-assessment of compliance in terms of number of abrocitinib-free days since the last visit.

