6.2 SAFETY ENDPOINTS

Incidence and severity of all adverse events including serious adverse events (SAEs). The reporting of safety data will be in accordance with Pfizer Data Standards.

Variable	Role	Data source(s)	Operational definition
Occurrence of adverse events	Safety outcome	Case records	Number and percentage of SOC and PT according to maximal grade of adverse event (patient based)
Occurrence of adverse drug reactions	Safety outcome	Case records	Number and percentage of SOC and PT according to maximal grade of adverse drug reaction (patient based)
Occurrence of serious adverse events	Safety outcome	Case records	Number and percentage of SOC and PT according to maximal grade of serious adverse event (patient based)
Occurrence of serious adverse drug reactions Safety outcome		Case records	Number and percentage of SOC and PT according to maximal grade of serious adverse drug reaction (patient based)
Reason for seriousness	Safety outcome	Case records	Number and percentage for each reason (event based)
Occurrence of scenarios involving drug exposure Safety outcome		Case records	Number and percentage (patient based)
Reason for scenario involving drug exposure	Safety outcome	Case records	Number and percentage for each reason (event based)
Worst outcome	Safety outcome	Case records	Number and percentage (patient based), order: recovered,

			recovered with sequelae, not recovered, unknown, fatal
Action taken	Safety outcome	Case records	Number and percentage for each reason (event based)
Type and results of performed laboratory checks	Potential confounder, potential subgroup identifier, safety outcome	Case records	Summary statistics (n, mean, median, standard deviation, minimum and maximum) of the minimal and maximal value per patient, respectively

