6.3 OTHER ENDPOINTS

Variable	Role	Data source(s)	Operational definition	
AD-treatment with abrocitinib and/or without topicals – total days	Exposure, Potential confounder, potential subgroup identifier	Case records	Date of last treatment – date of first treatment +1 Summary statistics (n, mean, median, standard deviation, minimum and maximum)	
AD-treatment with abrocitinib and/or without topicals – stratified by abrocitinib dose Exposure, Potential confounder, outcome, potential subgroup identifier		Case records	Date of last treatment – date of first treatment +1 Summary statistics (n, mean, median, standard deviation, minimum and maximum) stratified by the abrocitinib dose most often applied during the study	
Age (Year of birth)	Baseline characteristics, potential confounder, potential subgroup identifier	Case records	Age=year of IC – year of birth Summary statistics (n, mean, median, standard deviation, minimum and maximum)	
Sex	Baseline characteristics, potential confounder, potential subgroup identifier	Case records	Frequency analysis	
Height Baseline characteristics		Case records	Summary statistics (n, mean, median, standard deviation, minimum and maximum)	
Weight Baseline characteristics		Case records	Summary statistics (n, mean, median, standard deviation, minimum and maximum)	
Highest level of education	Baseline characteristics, potential confounder	Case records	Frequency analysis	
Ethnicity Baseline characteristics		Case records	Frequency analysis	

Occupational status	Baseline characteristics	Case records	Frequency analysis
Alcohol consumption status	Baseline characteristics, potential confounder	Case records	Frequency analysis
Insurance type	Baseline characteristics	Case records	Frequency analysis
Presence of family history of atopic diseases	Baseline characteristics, potential confounder, potential subgroup identifier	Case records	Frequency analysis
History of herpes simplex and/or eczema herpeticum and/or herpes zoster	Baseline characteristics	Case records	Frequency analysis
Vaccination status (Herpes zoster, Covid-19, Influenza Varicella)	Baseline characteristics	Case records	Frequency analysis
Age at initial diagnosis of AD	Baseline characteristics, potential confounder	Case records	Age at initial diagnosis =year of initial diagnosis – year of birth 1. Summary statistics (n, mean, median, standard deviation, minimum and maximum) 2. Categorical: < 12 y, 12-<18 y and ≥ 18 y

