Smoking history and current smoking status	Baseline characteristics, potential confounder	Case records	Frequency analysis
Renal and/or liver impairment	Baseline characteristics	Case records	Frequency analysis
Comorbidities at baseline	Baseline characteristics, potential confounder, potential subgroup identifier	Case records	Frequency analysis
If positive anamnesis at baseline exists: Improvement of (allergic) asthma symptoms from baseline	Baseline characteristics, potential confounder, potential subgroup identifier	Case records	Frequency analysis
If positive anamnesis at baseline exists: Improvement of (allergic) rhinitis symptoms from baseline	Baseline characteristics, potential confounder, potential subgroup identifier	Case records	Frequency analysis
If positive anamnesis at baseline exists: Improvement of polyposis nasi symptoms from baseline	Baseline characteristics, potential confounder, potential subgroup identifier	Case records	Frequency analysis
If positive anamnesis at baseline exists: Improvement of alopecia areata from baseline Baseline characteristics, potential confounder, potential subgroup identifier		Case records	Frequency analysis

If positive anamnesis at baseline exists: Improvement of chronic hand eczema symptoms from baseline	Baseline characteristics, potential confounder, potential subgroup identifier	Case records	Frequency analysis
If positive anamnesis at baseline exists: Improvement of prurigo nodularis symptoms from baseline	Baseline characteristics, potential confounder, potential subgroup identifier	Case records	Frequency analysis
Previous treatments for diagnosed AD	Baseline characteristics, potential confounder, potential subgroup identifier	Case records	Frequency analysis
Concomitant treatment of AD (and dosage)	Baseline characteristics, Exposure, explorative outcome, potential confounder, potential subgroup identifier	Case records	Frequency analysis and Summary statistics (n, mean, median, standard deviation, minimum and maximum) for dose
Concomitant (non-AD) treatment	Baseline characteristics, outcome, potential confounder, potential subgroup identifier	Case records	Frequency analysis with respect to level 1 and level 2 of ATC codes
Dosage of abrocitinib used	Exposure, potential confounder, explorative outcome variable, potential subgroup identifier	Case records	Summary statistics (n, mean, median, standard deviation, minimum and maximum)

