8.2.1 Safety Analyses

Treatment-emergent adverse events are adverse events which worsen or start after start of treatment with abrocitinib but no later than 28 days after end of treatment with abrocitinib.

In addition to the analysis of treatment-emergent adverse events and drug-related adverse events as specified in 6.2 adverse events which occurred under another systemic treatment, following cessation of abrocitinib, will be given and presented in a separated listing. Number and percentage of SOC and PT will be presented according to maximal grade.

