Outcome **Analysis Set Supports Missing Data** Subgroups Statistical Method Covariates/ Strata Protocol **Objective** Number baseline)/score at baseline*100 Mann-Whitney-U test for subgroups Change of EuroQol five-(score at respective FAS, mFAS, PP All None Excluded dimensional-five level visit - score at (EQ-5D-5L) from baseline)/score at 21 baseline baseline*100 Mann-Whitney-U test for subgroups Change of PBI from FAS, mFAS, PP All (score at respective None Excluded visit - score at baseline baseline)/score at 22 baseline*100 Mann-Whitney-U test for subgroups Patient's satisfaction FAS, mFAS, PP All Frequency tables for None Excluded satisfaction with with treatment (PBI after baseline) effectiveness and tolerability 23 Chi-Square test respective Fisher's exact test for subgroups Number of days with FAS, mFAS, PP All Excluded Summary statistics (n, None topical-treatment use mean, median, standard deviation, (TCS, TCI) 24 minimum and maximum) Mann-Whitney-U test for subgroups Number of days with FAS, mFAS, PP All Summary statistics (n, None Excluded emollients use mean, median, standard deviation, 25 minimum and maximum)

Outcome	Analysis Set	Supports Protocol Objective Number	Subgroups	Statistical Method	Covariates/ Strata	Missing Data
				Mann-Whitney-U test for subgroups		
AD-treatment with abrocitinib and/or without topicals – total days	FAS, mFAS, PP	26	All	Summary statistics (n, mean, median, standard deviation, minimum and maximum) Mann-Whitney-U test for subgroups	None	Excluded
AD-treatment with abrocitinib and/or without topicals – stratified by abrocitinib dose	FAS, mFAS, PP	27	All	Summary statistics (n, mean, median, standard deviation, minimum and maximum) Mann-Whitney-U test for subgroups	None	Excluded
Number of flares	FAS, mFAS, PP	28	All	Summary statistics (n, mean, median, standard deviation, minimum and maximum) Mann-Whitney-U test for subgroups	None	Excluded

All explorative endpoints mentioned in section 6.3 will be analyzed for FAS and all subgroups, respectively. Safety enpoints, as given in section 6.2 will be analyzed for SAF.

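### Dose-stratified exposure credits a dose switcher's whole treatment span to the most frequent dose, so time at 50, 100 and 200 mg is misstated for switchers

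*SAP*

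**What the plan says.** **Exposure.** SAP 6.3 has two treatment-duration rows. Both use the same formula, "Date of last treatment – date of first treatment +1". The second is "stratified by the abrocitinib dose most often applied during the study", which gives each patient one span and one dose stratum.

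**Dosage.** A separate row in SAP 6.3 covers the abrocitinib dose used, with the role "Exposure, potential confounder, explorative outcome variable, potential subgroup identifier". Its planned output is n, mean, median, SD, minimum and maximum. It gives no count per dose level and does not say whether the unit is the patient or the visit.

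**Dose changes.** SAP 5.4 expects them: its dose-sequence subgroup lists four switch sequences as well as unswitched classes. Protocol 9.2.4.5 collects the "stop date of previous dosage, start date of new dosage" and the reason for the switch. The reasons it names are lack of efficacy and intolerability.

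**Subgroups.** SAP 8.2.3 states: "All explorative endpoints mentioned in section 6.3 will be analyzed for FAS and all subgroups, respectively". On safety it says only: "Safety enpoints, as given in section 6.2 will be analyzed for SAF".

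**Adverse events.** SAP 6.2 tabulates events by system organ class, preferred term and maximal grade, plus seriousness, outcome and action taken. None of these rows has a dose dimension. SAP 8.2.1 ties treatment emergence to the drug, not to the dose at onset: "Treatment-emergent adverse events are adverse events which worsen or start after start of treatment with abrocitinib", up to 28 days after stopping.

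**The concern.** How abrocitinib is dosed and actually taken is an explorative objective (Protocol 8, SAP 1.3), and usage is part of the content of both interim analyses (SAP 2). The dose-stratified duration is the SAP's only variable meant to show treatment time by dose. For a switcher it does not do so: days at the less frequent dose are counted under the other one.

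A reader who takes the table as time at each dose would get the wrong denominators for any later rate. The distortion could also run in either direction, depending on when patients switch. Because the specified safety tables carry no dose information, they give no other route to a dose-specific picture.

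**Working it through.** The documents give no figure to reproduce. There is no formal sample size calculation and no expected switching rate. What follows is the rule as written, then an illustration on stated assumptions.

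**Inputs from the documents:** N = 750 (Protocol 9.5); observation of 12 months, month-12 target day 365 (Protocol 9.7); span formula and most-frequent-dose rule (SAP 6.3).

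**Assumptions:** every patient is treated for 365 days; all start on a dose A; a share *s* switches once to a dose B after *t* days; the dose most often applied means the dose with most days. The SAP does not say whether days, visits or prescriptions are counted.

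**One patient.** With 84 days at one dose and 281 at another (assumed), the row records 365 days at the second dose and 0 at the first: 84/365 = 23% of the time is misfiled. With *k* doses the misfiled share can approach 1 − 1/*k*, which is 1/2 for two doses and 2/3 for three. For a patient who never switches it is 0.

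**All patients.**
- True days at A = N × [(1 − s) × 365 + s × t]; true days at B = N × s × (365 − t).
- Rule as written, if t < 365 − t: A = N × (1 − s) × 365 and B = N × s × 365. Otherwise A = N × 365 and B = 0.
- Share of all days misassigned = s × min(t, 365 − t)/365.

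Worked case, s = 0.30 and t = 91, dividing days by 365.25 for patient-years (PY):
- True A = 750 × (255.5 + 27.3) = 212,100 days = 581 PY. True B = 750 × 0.30 × 274 = 61,650 days = 169 PY.
- Rule A = 750 × 0.70 × 365 = 191,625 days = 525 PY (−10%). Rule B = 750 × 0.30 × 365 = 82,125 days = 225 PY (+33%).
- Misassigned = 0.30 × 91/365 = 7.5%.

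| s | t (day) | A true → rule (PY) | B true → rule (PY) | Days misassigned |
|---|---|---|---|---|
| 0.10 | 30 | 681 → 675 (−1%) | 69 → 75 (+9%) | 0.8% |
| 0.30 | 91 | 581 → 525 (−10%) | 169 → 225 (+33%) | 7.5% |
| 0.30 | 182 | 637 → 525 (−18%) | 113 → 225 (+99%) | 15.0% |
| 0.30 | 273 | 693 → 749 (+8%) | 57 → 0 (−100%) | 7.6% |
| 0.50 | 182 | 562 → 375 (−33%) | 188 → 375 (+99%) | 24.9% |
| 0.50 | 273 | 655 → 749 (+14%) | 94 → 0 (−100%) | 12.6% |

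The first and fifth rows are the ends of the range for misassigned days over s = 10% to 50% and t = 30 to 273.

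**Interruptions.** The first-to-last span also counts gaps as treatment, for switchers and non-switchers alike. An assumed 28-day gap overstates on-drug days by 365/337 − 1 = 8.3%.

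**The case against.** Four points can be made for the plan.

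1. *Exposure by dose is partly readable.* This stands. A reader might infer that exposure at 50, 100 or 200 mg cannot be read at all; the documents do not support that. Patients on one dose throughout fall in the right stratum. SAP 8.2.3 also applies all subgroups, including dose sequence, to the total-days row, so duration will appear for unswitched 200 mg and 50 mg patients if the class has at least 20. No unswitched 100 mg class appears in the list as read, but a reading loss there cannot be excluded and nothing here rests on it. What the sequence table cannot do is divide a switcher's days between doses.

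2. *The row may be meant as duration by predominant dose.* That is a legitimate description, and no days are lost from the total-days row. But the label says stratified by dose and does not warn the reader.

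3. *The dosage summary is not blind to the mix of doses.* This stands. A reader might argue that a mean of 100 mg hides whether everyone takes 100 mg or two thirds take 50 mg and one third 200 mg, since (2/3) × 50 + (1/3) × 200 = 100. The planned median, SD, minimum and maximum separate these cases: 100, 0, 100 and 100 against 50, about 71, 50 and 200. What remains is that counts per level are not planned.

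4. *Safety by dose may exist elsewhere.* SAP 8.1 speaks generally of comparing variables across subgroups, SAP 6.2 refers to sponsor data standards, and the table shells are in a separate file (SAP 9) that was not available. So a reader should not infer that adverse events will never be shown by dose, only that the SAP text does not specify it. It is also fair that no objective asks for safety by dose, and that dose is chosen by the physician, so such rates are confounded.

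**Conclusion.** The point holds for switchers. As written, SAP 6.3 misstates person-time at each dose for every patient who changes dose, by up to about half of that patient's days with two doses, taking the most frequent dose as the one with most days. The total effect cannot be fixed from the documents because no switching rate is given. On the assumptions above it runs from 0.8% to 24.9% of all treatment days. Time at the second dose can be off by anything from −100% to +99%.

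The dosage row lacks a count per level, and no adverse event table by dose is specified in the SAP text; these are lesser gaps. The point concerns reporting of explorative outcomes. It does not touch the month-3 primary endpoints and says nothing about which dose is appropriate.

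**What to change.** **SAP 6.3, exposure.** For each patient, sum the days at each dose from the documented dose start and stop dates, and report days and patient-years per dose. Keep the existing table only if it is labelled as duration by predominant dose, with a statement of what is counted to decide predominance.

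**SAP 6.3, dosage.** Add a frequency table of dose level, including off drug, at each visit.

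**SAP 6.2 and 8.2.1, as a secondary descriptive addition.** Tabulate treatment-emergent and serious adverse events by dose at onset, as follows:
- Match numerator and denominator: either on-drug events over on-drug days, or both including the 28 days after stopping. Attributing post-stop events to the last dose while counting only on-drug days would inflate the rates, most of all for short exposures.
- Apply the 20-patient rule of SAP 5.4.
- Flag events or dose changes with imputed dates, because SAP 7 sets a missing day to the 15th and a missing day and month to mid-year, which can shift the dose at onset.
- State that dose is not randomised.

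**Cost.** SAP wording and programming only, since the dose-change dates are already collected. The downside is one extra table set and dose-specific safety figures that need a confounding caveat.

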- c. Comorbidities of interest (atopic diseases, malignancies, cardiovascular diseases, alopecia areata, prurigo nodularis, hand eczema). If baseline visit had a positive anamnesis for the following: (allergic) asthma, (allergic) rhinitis, polyposis nasi, chronic hand eczema, prurigo nodularis and alopecia areata, a qualitative outcome assessment will be done (ie, assessment of investigator if comorbidity improves during abrocitinib therapy).
- d. Previous therapies and reasons for termination of previous treatments.
- e. Reasons for starting treatment with abrocitinib.
- f. Number of AD flares one year before start of treatment with abrocitinib and during observational period.

- g. Number of absent days at work/study caused of AD one year before start of treatment with abrocitinib and during observational period.
- h. Number of AD hospitalizations in the observation period and one year before start of treatment with abrocitinib.

[figure not shown]
Documentation of safety:

- a. Safety: incidence of adverse events and serious adverse events.
- b. Severity of adverse events (when applicable) (as assessed by the investigator according to the following categories:
 - Mild: Does not interfere with the patient's usual function.
 - Moderate: Interferes to some extent with the patient's usual function.
 - Severe: Interferes significantly with the patient's usual function.

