9.2.3. Study Period

The planned observation period of each patient is 12 months. In this time period up to 6 visits will be documented.

Figure 2. Study Period Start of Month 1 data Month 3 data Month 6 data Month 9 data Month 12 data collection collection collection collection 9 12 0 3 6 1

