9.2.3.2. Schedule of Activities

The recommended schedule of activities table provides an overview of the visits that may be documented. Refer to Section 9.2.4 Assessments section of the protocol for detailed information on each documentation and assessment. As this is a non-interventional study none of these visits are mandatory and every visit should be scheduled according to clinical practice. According to clinical practice the HCP may schedule additional visits to those listed on the schedule of activities, in order to conduct evaluations or assessments required to protect the well-being of the patient.

Table 1. Recommended Schedule of Activities

Study period based on	Baseline	Month	Month	Month	Month	Month
routine visits	(Enroll ment)	1	3	6	9	12 End of Study (EoS)
Visit Number	1	2	3	4	5	6
Informed consent	X					
Inclusion/exclusion criteria	X					
Demographic data of patient (age, sex, weight, height, ethnicity, smoker/non- smoker, education, occupation, alcohol consumption, insurance type)	X					
Family history of atopic diseases	X					
Clinical history (Herpes simplex, eczema herpeticum, herpes zoster)	X					
Renal and/or liver impairment	X					
Vaccination status (Herpes zoster, Covid-19, Influenza, Varicella)	X					X
Age at initial diagnosis of AD	X					
Previous treatments for diagnosed AD	X					
Current comorbidities of interest (atopic diseases, malignancies, cardiovascular diseases)	X					
If positive anamnesis at baseline exists: Improvement of asthma symptoms from baseline						X

Study period based on routine visits	Baseline (Enroll ment)	Month 1	Month 3	Month 6	Month 9	Month 12 End of Study (EoS)
If positive anamnesis at baseline exists: Improvement of allergic rhinitis symptoms from baseline						X
If positive anamnesis at baseline exists: Improvement of polyposis nasi symptoms from baseline						X
If positive anamnesis at baseline exists: Improvement of alopecia areata from baseline						X
If positive anamnesis at baseline exists: Improvement of prurigo nodularis from baseline						X
If positive anamnesis at baseline exists: Improvement of hand eczema from baseline						X
Number of flares during the last 12 months (first visit) and since the last visit (regardless of Abrocitinib treatment status*)	X	X	X	X	X	X
Number of hospitalizations due to AD during the last 12 months (first visit) and since the last visit (regardless of Abrocitinib treatment status*)	X	X	X	X	X	X

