Number of absent days at work/study due to AD one year before start of treatment with Abrocitinib (first visit) and since the last visit	X	X	X	X	X	X

^{*} This includes patients who discontinued treatment with Abrocitinib.

Study period based on routine visits	Baseline (Enroll ment)	Month 1	Month 3	Month 6	Month 9	Month 12 End of Study (EoS)
(regardless of Abrocitinib treatment status*)						
Reasons for start of therapy with Abrocitinib	X					
Reasons for discontinuation of therapy with Abrocitinib		X	X	X	X	X
Compliance with Abrocitinib treatment		X	X	X	X	X
Dosage of Abrocitinib used	X	X	X	X	X	X
Reasons for prescribed dosage	X	X	X	X	X	X
Type and results of laboratory check controls	X	X	X	X	X	X
Adverse events		X	X	X	X	X
Concomitant treatment AD specific (type and dosage)	X	X	X	X	X	X
Number of days with topical- treatment use (TCS, TCI) & days with emollients use three months before start of treatment with Abrocitinib (first visit) and since the last visit (regardless of Abrocitinib treatment status*	X	X	Х	X	X	X
Concomitant (non-AD) treatment	X					
SCORAD	X	X	X	X	X	X
EASI	X	X	X	X	X	X

^{*} This includes patients who discontinued treatment with Abrocitinib.

Study period based on routine visits	Baseline (Enroll ment)	Month 1	Month 3	Month 6	Month 9	Month 12 End of Study (EoS)
IGA	X	X	X	X	X	X
Pruritus-NRS	X	X	X	X	X	X
PP-NRS	X	X	X	X	X	X
DLQI	X	X	X	X	X	X
POEM	X	X	X	X	X	X
MOS	X	X	X	X	X	X
PBI	X	X	X	X	X	X
EQ-5D-5L	X	X	X	X	X	X
HADS	X	X	X	X	X	X

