9.2.4.2. Disease Characteristics and Previous AD Treatments

At the baseline Visit (Visit 1) the presence of a family history of atopic diseases as well as a patient's clinical history regarding herpes simplex, herpes zoster, eczema herpeticum will be documented. Furthermore, the age at initial diagnosis of AD, previous treatments for diagnosed AD as well as current comorbidities of interest (atopic diseases: asthma, allergic rhinitis, food allergies, nasal polyps; malignancies, cardiovascular diseases) and concomitant non-AD specific treatments will be documented. At the baseline visit the number of flares as well as the number of hospitalizations and the number of absent days at work/study caused by AD during the last 12 months prior to start of abrocitinib will be documented. At each of the subsequent visits (Visit 2-6), the number of flares, the number of hospitalizations due to AD, as well as the number of absent days at work/study since the last documented visit will be captured.

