Compliance with abrocitinib treatment (patients' reported compliance)	potential confounder, explorative outcome	Case records	Frequency analysis
Reasons for start of abrocitinib therapy	Explorative outcome variable	Case records	Frequency analysis
Reasons for prescribed dose of abrocitinib therapy	Explorative outcome variable	Case records	Frequency analysis
Reasons for discontinuation of abrocitinib therapy	Explorative outcome variable	Case records	Frequency analysis
Number of flares	Explorative outcome variable	Case records	Summary statistics (n, mean, median, standard deviation, minimum and maximum)
Number of hospitalizations due to AD	Explorative outcome variable	Case records	Summary statistics (n, mean, median, standard deviation, minimum and maximum)
Number of absent days at work/study due to AD Explorative outcome variable		Case records	Summary statistics (n, mean, median, standard deviation, minimum and maximum)

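### Flares, AD hospitalisations and absent days are summarised as raw counts with no time denominator, so an unchanged rate can read as a reduction against the 12-month baseline

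*SAP*

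**What the plan says.** The three items are explorative endpoints. Protocol 9.1.1 pairs two periods for each; for flares it reads "Number of AD flares one year before start of treatment with abrocitinib and during observational period", and the items on absent days and hospitalisations are built the same way.

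The recall periods are in Table 1 of Protocol 9.2.3.2:

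- "Number of flares during the last 12 months (first visit) and since the last visit"
- "Number of hospitalizations due to AD during the last 12 months (first visit) and since the last visit"
- "Number of absent days at work/study due to AD one year before start of treatment with Abrocitinib (first visit) and since the last visit"

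Protocol 9.2.4.2 repeats this for Visits 2 to 6, for example "the number of absent days at work/study since the last documented visit will be captured". On duration, Protocol 9.2.3 says: "The planned observation period of each patient is 12 months".

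For the analysis, SAP 6.3 lists each count, including "Number of hospitalizations due to AD", with standard summary statistics of the number. It mentions no rate, person-time, offset or rule for incomplete follow-up. It also gives no time-point wording, whereas the score endpoints in SAP 6.1 are explicitly summarised at each time point. SAP 6.4 lists no covariates and SAP 7 in general imputes nothing. SAP 8.2.3 analyses the 6.3 endpoints in the FAS and all subgroups. The FAS (SAP 5.1) requires consent, eligibility and one dose, so patients with short follow-up are in it. SAP 8.1 compares numerical data between subgroups by the Mann-Whitney U test.

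**The concern.** A count means little without the time over which it was collected. Here the baseline number always stands for a year. The follow-up number stands for one inter-visit interval or for whatever part of the year was documented, depending on a choice the SAP leaves open. A reader who sets the two summaries side by side, as the protocol endpoint invites, would see fewer flares, admissions and lost days even if the underlying rate had not moved.

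The subgroup comparisons share the problem. Patients who switched from abrocitinib, for instance, are compared with those who stayed on it (SAP 5.4). If the groups are observed for different lengths of time, or have different gaps between documented visits, a test on raw counts partly compares observation time.

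The visit-window rule adds to this. When two routine visits fall in one window, SAP 1.1 keeps only the one nearer the target day. Since each count covers only the time since the last visit, dropping a visit can drop its events. SAP Appendix 1 carries information from additional documentation time points forward to the next scheduled visit, but does not clearly cover this case.

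**Working it through.** The plan gives no figure to reproduce: there is no event rate, dropout rate or sample-size calculation for these endpoints. The check asks what the specified summaries would show if the event rate did not change at all.

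**Inputs from the documents.** Baseline look-back: 12 months (Protocol 9.2.3.2). Target days: 1, 30, 91, 182, 273, 365 (SAP 1.1, Table 2). Month 12 window in the final analysis: day 302 to 393 (SAP 1.1, amended definition).

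**Assumed input.** Dropout of 10 to 40%, shown as a range.

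**Principle.** At a constant rate, expected follow-up count ÷ expected baseline count = observed time in years. Apparent reduction = 1 − observed time in years.

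**Reading A: counts shown per visit, no dropout.** Apparent reduction = 1 − gap/365.

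| Visit | Gap (days) | Share of baseline year | Apparent reduction |
|---|---|---|---|
| Month 1 | 30 − 1 = 29 | 7.9% | 92% |
| Month 3 | 91 − 30 = 61 | 16.7% | 83% |
| Month 6 | 182 − 91 = 91 | 24.9% | 75% |
| Month 9 | 273 − 182 = 91 | 24.9% | 75% |
| Month 12 | 365 − 273 = 92 | 25.2% | 75% |

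Interval length does all of this. Non-informative dropout adds nothing, because missing values are excluded. A missed visit lengthens the next recall interval, so one visit column can mix different exposure times.

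**Reading B: counts summed per patient.** Let d be the share who drop out. If they leave uniformly over the year, they contribute half a year on average, so the reduction is d × 0.5. If all leave at Month 3, it is d × (1 − 91/365) = d × 0.75.

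| d (assumed) | Uniform dropout | All leave at Month 3 |
|---|---|---|
| 10% | 5% | 7.5% |
| 20% | 10% | 15% |
| 30% | 15% | 22.5% |
| 40% | 20% | 30% |

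- Complete follow-up: the gaps sum to 29 + 61 + 91 + 91 + 92 = 364 days, so there is almost no bias. For one patient, a Month 12 visit anywhere in the window gives 302/365 = 0.83 to 393/365 = 1.08 of a year.
- Second interim analysis (IA2), patient observed only to Month 6: 1 − 182/365 = about 50%.

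**Check of the remedy.** A Poisson simulation (300,000 patients; rates of 1 and 4 per year; uniform dropout of 10, 20 and 30%; no effect) gave raw apparent reductions of 4.9 to 5.2%, 9.8 to 10.2% and 15.0 to 15.2%. Dividing by observed time gave −0.2% to +0.2%.

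**The case against.** The strongest reply is that follow-up is designed to match the look-back. Both are 12 months, Protocol 7.4 intends full observation whatever the treatment status, and Protocol 10.3 says that stopping abrocitinib is not withdrawal. A late Month 12 visit can even exceed a year. A reader might infer that follow-up is shorter by design, or that dropout by itself guarantees a false reduction. The documents support neither. The shortfall arises for dropouts, at interim cuts and within single visit intervals, and dropout is the mechanism only if counts are summed, which the SAP does not say.

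A reader might also infer that a planned before/after test is biased. No such test exists. SAP 6.3 specifies no change from baseline for these counts, SAP 4 sets no hypotheses, and the only tests are exploratory ones between subgroups. The misleading contrast would come from reading two descriptive summaries together.

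There are partial safeguards. For flares, SAP 8.2.3 also lists the per-protocol set (all visits completed), but SAP 5.3 uses it only if at least 10% of the mFAS is omitted. It is not listed for hospitalisations or absent days, and it would not cure the per-visit reading. The number of available observations is displayed. Table layouts are in a separate mock-up file (SAP 9) that is not among the documents and may settle the per-visit question.

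These replies limit the point but do not remove it. The SAP as written supplies no time denominator, and under either reading a raw count can show a fall that is only observation time.

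**Conclusion.** The point holds as a flaw in how three explorative endpoints are summarised, and it should be corrected. Under an unchanged rate, the artefact is about 75 to 92% if counts are shown per visit. If they are summed, it is about 5 to 20% (uniform dropout) or 7.5 to 30% (all dropouts leaving at Month 3) for dropout of 10 to 40%. It is about 50% at IA2 for a patient observed only to Month 6, and near zero with complete follow-up.

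The per-visit figures rest only on the nominal visit days. The summed figures rest on assumed dropout and a constant rate, so the actual size cannot be fixed from the documents. The size of the subgroup distortion is likewise unknown; it depends on how far observation time differs between groups. Primary and secondary results are not affected.

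**What to change.** In SAP 6.3 and 8.2.3:

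1. State whether follow-up counts are per visit or summed per patient, and what happens to counts from visits discarded by the window rule.
2. For each of the three items, report total events (or days) divided by the observed time that the documented count items cover, as a rate per patient-year with 95% CI, beside the 12-month baseline rate. The denominator should not simply run from Day 1 to the last visit, because time at which the item was not recorded would then dilute the rate.
3. Show the distribution of observed follow-up time, overall and by subgroup.
4. Use rates, not raw counts, in the exploratory subgroup comparisons.
5. Add a sensitivity summary in patients with complete 12-month follow-up.

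A pre/post rate ratio from a Poisson or negative binomial model with a log-time offset is optional in a descriptive study.

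The cost is SAP wording and minor programming; visit dates are already needed for the windows. Rates do not remove bias from informative dropout or regression to the mean, so the report should say that a lower rate after baseline is not in itself evidence of a drug effect.
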